6.4.3 Prior distribution

To complete the specification of the Bayesian model we specify prior distributions for the model parameters. We assume $\gamma_k \sim \text{Normal}(0, 10^6)$ and $\beta \sim \text{Normal}(0, 10^6)$. These priors impose essentially no information on the analysis due to the extremely large variances of their distributions. If the categorical representation of tumor size is used then a multivariate prior will be assumed for β .

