6.4 Statistical analysis of clinical success

It has been noted in the literature that if a tumor reoccurs in the same site, it typically does so within the first two years [4]. There is some evidence of reoccurrence as far out as 40 months but that is based on limited data and beyond 4 years there is no follow-up data [4]. For the purpose of this study, the analysis of the clinical outcome will be based on a 2-year endpoint. As with the determination of technical success,

a literature-based benchmark will be used in lieu of a concurrent control. Results in [5] suggest that the cumulative incidence of reoccurrence by 2 years is around 26.4% and by 4-years is around 37.8%. However, these results were not stratified by tumor size, which is known to be a very strong predictor of clinical success. In [4], reoccurrence rates of 14.1%, 24.5%, and 58.1% were reported for the small, medium and large tumor groups. However, these rates were evaluated over variable lengths of follow-up. The proportion of cases expected in the small, medium, and large categories are 12.9%, 41.9%, and 45.2% respectively (based on past clinical experience). The benchmark number to be used for the overall group comparison is the weighted average of these proportions with the above recurrence rates, which equals 24.1%. Because the failure rate data in [4] involve 1817 observations, we use this number as a basis for quantifying the precision in the baseline. Computing the lower end-point of a 95% confidence interval, we obtain $q_{\text{base}} = 0.2217$ as our ideal or most conservative benchmark against which to compare outcomes under PGP. This value is conservative even beyond the buffer provided by the allowance for uncertainty in its true value via the confidence interval end-point calculation as the follow-up times in [4] were shorter on average than 2-years.

For both the conservative and less conservative benchmarks, the overall assessment of the clinical success of PGP will be evaluated using the hypothesis test:

$$H_0: q_{\text{RFA}} \geq q_{\text{base}} \text{ against the alternative } H_1: q_{\text{RFA}} < q_{\text{base}}$$

where q_{RFA} is the probability of reoccurrence by 2-years of follow-up.

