6.4.2 Model for multinomial outcome: generalized logistic regression

The distribution of y_i is multinomial with five categories:

$$y_i | \theta_i \sim \text{Multinomial}_5(1, \theta_i)$$

where $\theta_i = (\theta_{i0}, \theta_{i1}, \theta_{i2}, \theta_{i3}, \theta_{i4})$ is the vector of probabilities associated with the five possible outcomes for patient i . Models for multinomial outcomes are characterized by the way in which the elements of θ_i are mapped to the predictors. One commonly used specification is generalized logistic regression in which each component of θ_i is compared to all other components through a logit link function by supposing:

$$\theta_{ik} = \lambda_{ik} / (\lambda_{i0} + \lambda_{i1} + \lambda_{i2} + \lambda_{i3} + \lambda_{i4})$$

and $\log(\lambda_{ik}) = \gamma_k + \beta x_i$ for $k = 0, \dots, 4$. A key feature of this specification is that the Bayesian software package JAGS will impute any y_{ik} whose value is missing. To implement this feature any values of y_{ik} that are missing will be represented as NA in the analytic data set. We note that the above specification assumes the proportional odds assumption that the effects of all terms other than γ_k does not depend on k holds. This is an assumption whose legitimacy can be tested empirically.

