6.4.4 Evaluation of hypothesis test and other summaries of the posterior distribution

We wish to average the 2-year survival probability across the study patients, given by

$$q_{\text{RFA}} = 1 - n^{-1} \sum_{i=1}^n \theta_{i4}$$

where based on the above generalized logit model the probability of clinical success at 2-years for patient i is given by

$$\theta_{i4} = \frac{\exp(\gamma_4 + \beta x_i)}{\exp(\gamma_0 + \beta x_i) + \exp(\gamma_1 + \beta x_i) + \exp(\gamma_2 + \beta x_i) + \exp(\gamma_3 + \beta x_i) + \exp(\gamma_4 + \beta x_i)}$$

The posterior probability of clinical success, $\Pr(q_{\text{RFA}} < q_{\text{base}} | y_1, \dots, y_n, x_1, \dots, x_n)$, is then determined by evaluating q_{RFA} for a large number of draws from the posterior distribution of the model parameters and evaluating the Monte-Carlo average

$$\Pr(q_{\text{RFA}} < q_{\text{base}} | y_1, \dots, y_n, x_1, \dots, x_n) \cong n^{-1} \sum_{j=1}^{n_{\text{sim}}} I(q_{\text{RFA}}^j < q_{\text{base}})$$

where q_{RFA}^j denotes the value of q_{RFA} computed on the j th of n_{sim} draws of the model parameters from their joint posterior distribution. The mean, standard deviation, and 95% interval estimates of q_{RFA} will be similarly determined.

Because the chance of clinical success likely varies continuously with tumor size, we can substitute the mean tumor size for the benchmark population in [4] for x_i to essentially control for tumor size. Alternatively, we may substitute x_i with the corresponding small, medium, and large tumor size subgroup mean and in so-doing evaluate the posterior probability with closer control for the tumor size distribution. For the subgroup analyses that compare the performance of RFA-GP on the small, medium and large tumor

subgroups we may estimate $\Pr(q_{\text{RFA}} < q_{\text{base}} \mid \text{size} = s, y_1, \dots, y_n, x_1, \dots, x_n)$ separately for each subgroup $s \in \{\text{small, medium, large}\}$.

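### The Normal(0, 10^6) priors are not uninformative on the recurrence scale, and estimates made before follow-up is complete become overconfident when a 6-month interval has no recurrence

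*SAP*

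**What the plan says.** SAP section 6.4.2 describes the outcome thus: "The distribution of y_i is multinomial with five categories". Four categories are 6-month intervals of recurrence and the fifth is freedom from recurrence at 24 months. Each category has its own intercept gamma_k, with k from 0 to 4 and none fixed as reference. The size effect beta is common to all categories: the model assumes that "the effects of all terms other than γ_k does not depend on k holds".

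Section 6.4.3 gives every gamma_k and beta a Normal(0, 10^6) prior and comments: "These priors impose essentially no information on the analysis". The reason it gives is that the variances are very large. So 10^6 is a variance, and the SD is 1000 on the log scale.

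The target in section 6.4 is q_RFA, "where q_{RFA} is the probability of reoccurrence by 2-years of follow-up", compared with q_base = 0.2217. The same section wants this to be estimable at any time once the 2-year recruitment phase ends, with the Bayesian model imputing the later 6-month statuses of lesions not yet followed for 24 months. Section 6.4.4 adds optional posterior probabilities by size group. Section 6.4.5 gives a continuation-ratio fallback without a separate prior. No posterior-probability threshold for success and no prior sensitivity analysis are stated.

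**The concern.** A very large variance on a logit does not mean a vague prior on a probability. With SD 1000, one of the five exponentiated intercepts almost always dwarfs the others, so the prior says that one category is nearly certain, without saying which. Where events are observed, the data override this. Where an interval has none, nothing in the prior keeps its risk away from zero.

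The early estimates depend on just those interval risks. The last interval is informed only by the lesions enrolled first, so it is often empty, and its estimated risk is then carried to every lesion still in follow-up. At stake is the honesty of the early posterior probability and of its 95% interval.

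**Working it through.** **Inputs.** Prior SD 1000, five categories, q_base = 0.2217 and 62 lesions are from the SAP (sections 6.4 to 6.4.6). The 0.95 posterior cut-off, the cohort sizes and the constant hazard are assumptions.

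**1. The SAP's power figure.** Section 6.4.6 states 80% power at q = 0.105. The exact binomial rule that rejects at 8 or fewer recurrences of 62 has P(X <= 8 | 0.2217) = 0.048 and P(X <= 8 | 0.105) = 0.80. The figure is reproduced.

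**2. Prior on q.** With q = 1 - exp(gamma_4) / sum of exp(gamma_k), drawing the gammas with SD 1000 gives P(q > 0.99) = 0.80 and P(q < 0.01) = 0.20, with about 0.2% between. The same prior on the four continuation-ratio logits of section 6.4.5 gives 93.7% and 6.1%.

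**3. Complete data.** In the flat-logit limit, r recurrences give q ~ Beta(r, 62 - r), with mean r/62. Pr(q < 0.2217) is:

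| r | SAP priors | Beta(1/2, 1/2) on q |
|---|---|---|
| 8 | 0.974 | 0.967 |
| 9 | 0.945 | 0.932 |

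At a 0.95 cut-off both give the rule of step 1: at most 8 of 62.

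**4. An empty interval.** Let h_k be the risk in interval k given no earlier recurrence, so q = 1 - product of (1 - h_k). With n_k lesions at risk and d_k recurrences, the flat-logit limit gives h_k ~ Beta(d_k, n_k - d_k). At d_k = 0 this collapses to zero. With the actual SD of 1000 and 0 recurrences among 14 lesions at risk, about 99% of the posterior lies below 0.000001. The exact one-sided 95% upper limit is 1 - 0.05^(1/14) = 0.19.

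**5. How often the last interval is empty.** With constant hazard and q = 0.2217, a lesion recurs in months 18-24 with probability 0.7783^0.75 - 0.7783 = 0.8286 - 0.7783 = 0.0503. In four even cohorts, 15 or 16 of the 62 lesions have 24 months of follow-up. The interval is empty with probability 0.9497^15 = 0.46 (or 0.9497^16 = 0.44). With only 7 such lesions it is 0.9497^7 = 0.70.

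**6. Consequence at the first permitted analysis.** Simulation with true q = 0.2217 (no benefit), known recurrence-free intervals retained, and success taken as Pr(q < 0.2217) > 0.95. The comparator is Dirichlet(1/8, 1/8, 1/8, 1/8, 1/2), which is Beta(1/2, 1/2) on q. Ranges show the spread between repeated runs.

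| Lesions with 6/12/18/24 months | False success, SAP priors | False success, Dirichlet | 95% interval coverage, SAP priors | Coverage, Dirichlet |
|---|---|---|---|---|
| four even cohorts | about 11% | about 7% | about 90% | 93-94% |
| 20/20/15/7 | 16-18% | about 6% | 86% | 96% |

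With all 62 lesions followed for 24 months, false success is about 5% under both.

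**7. Size subgroups.** Because beta is common, exp(beta x_i) multiplies numerator and denominator in section 6.4.4 and cancels. With illustrative counts of 0/8, 4/26 and 5/28, every size group gets the pooled mean of 9/62 = 0.145 and Pr(q < 0.2217) of about 0.947. Only with a category-specific size effect (Pr = 0.99997) or a separate fit (0.9999) does the 0/8 group go to nearly 1.

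**The case against.** The best defence is that the sentence refers to the analysis, and for the complete 62-lesion analysis it is fair: the posterior mean is the observed proportion and the rule matches the exact test. An empty interval then does no harm, because q sums over the four intervals. The surplus intercept is also harmless for q, which depends only on differences between intercepts, and the priors are proper. All of this stands, and it confines the point to incomplete follow-up.

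The Dirichlet comparator is not a full cure either. Its false success with even cohorts is 7%, and a weight of 1/8 still leans towards low interval risk: after 0/8 in the first interval, Beta(0.125, 8.875) has 77% of its mass below 1%. That also stands. It supports a sensitivity analysis rather than reliance on one prior.

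A reader might infer more from the subgroup plan, "For the subgroup analyses that compare the performance of RFA-GP on the small, medium and large tumor" groups: that a group with no recurrences would be declared a certain success. The documents do not support this. The model as written gives each group the pooled estimate, the subgroup probabilities are optional and unpowered, and no threshold is stated. The size of the small-tumour group is itself uncertain. The printed shares and rates average 0.129 x 14.1 + 0.419 x 24.5 + 0.452 x 58.1 = 38.3%, not the stated 24.1%, whereas reversed shares give 24.1%. The group may therefore have about 8 or about 28 lesions. At a 14.1% true rate, no recurrence has probability 0.30 in 8 lesions and 0.014 in 28.

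**Conclusion.** The point holds in limited form. The statement that the priors carry essentially no information is wrong for q, and the error reaches an analysis that the SAP plans: estimation before all lesions have 24 months of follow-up. There the planned priors raise false success by about 4 percentage points with even cohorts and by about 10 to 12 points when few lesions have long follow-up. Coverage of the 95% interval falls to about 90% and 86%.

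These sizes rest on the assumed cohorts, constant hazard and 0.95 cut-off. The cohorts follow the SAP's 2-year recruitment. Protocol section 9.2 expects enrolment in 12 months; on that schedule more lesions would have long follow-up at the same date and the effect would be smaller. The complete-data result and its power are not in question. An empty size subgroup would get a posterior probability near 1 only under a model that section 6.4.2 does not specify. This is a modest point that is cheap to repair.

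**What to change.** - In section 6.4.3, delete the sentence on no information, or replace it with the prior that the model implies for q.
- Fix one category as reference, for example gamma_4 = 0.
- For the overall analysis without size, use a prior that is proper and weakly informative on the probability scale, such as Dirichlet(1/8, 1/8, 1/8, 1/8, 1/2).
- When size is in the model, and for the section 6.4.5 fallback, use an equivalent moderate-variance prior on the interval logits. Its location needs care. Five intercepts centred at zero imply a prior mean for q of 0.80 at any variance, and a Dirichlet with all weights 1 would tighten the rule to 5 or fewer of 62 and cut power at 0.105 to 0.36.
- If size-specific results are wanted, let the size effect vary by category. The new prior is then essential, because the collapse would otherwise reach empty size groups.
- Report a prior sensitivity analysis with every estimate made before follow-up is complete, and state the posterior threshold for success.

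The cost is SAP wording and a few lines of model code. With the Dirichlet above, the complete-data rule stays at 8 or fewer of 62 (at the assumed 0.95 cut-off) and power stays at 80%. The downside is that early and subgroup intervals become wider and early analyses are less likely to show success.

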6.4.4 Evaluation of hypothesis test and other summaries of the posterior distribution

We wish to average the 2-year survival probability across the study patients, given by

$$q_{\text{RFA}} = 1 - n^{-1} \sum_{i=1}^n \theta_{i4}$$

where based on the above generalized logit model the probability of clinical success at 2-years for patient i is given by

$$\theta_{i4} = \frac{\exp(\gamma_4 + \beta x_i)}{\exp(\gamma_0 + \beta x_i) + \exp(\gamma_1 + \beta x_i) + \exp(\gamma_2 + \beta x_i) + \exp(\gamma_3 + \beta x_i) + \exp(\gamma_4 + \beta x_i)}$$

The posterior probability of clinical success, $\Pr(q_{\text{RFA}} < q_{\text{base}} | y_1, \dots, y_n, x_1, \dots, x_n)$, is then determined by evaluating q_{RFA} for a large number of draws from the posterior distribution of the model parameters and evaluating the Monte-Carlo average

$$\Pr(q_{\text{RFA}} < q_{\text{base}} | y_1, \dots, y_n, x_1, \dots, x_n) \cong n^{-1} \sum_{j=1}^{n_{\text{sim}}} I(q_{\text{RFA}}^j < q_{\text{base}})$$

where q_{RFA}^j denotes the value of q_{RFA} computed on the j th of n_{sim} draws of the model parameters from their joint posterior distribution. The mean, standard deviation, and 95% interval estimates of q_{RFA} will be similarly determined.

Because the chance of clinical success likely varies continuously with tumor size, we can substitute the mean tumor size for the benchmark population in [4] for x_i to essentially control for tumor size. Alternatively, we may substitute x_i with the corresponding small, medium, and large tumor size subgroup mean and in so-doing evaluate the posterior probability with closer control for the tumor size distribution. For the subgroup analyses that compare the performance of RFA-GP on the small, medium and large tumor

subgroups we may estimate $\Pr(q_{\text{RFA}} < q_{\text{base}} \mid \text{size} = s, y_1, \dots, y_n, x_1, \dots, x_n)$ separately for each subgroup $s \in \{\text{small, medium, large}\}$.

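### The optional mean-size substitution for q_RFA yields the risk at one tumor size, while the benchmark is an average of size-specific risks; once size acts in the model, the two differ by roughly 2 points under assumed sizes

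*SAP*

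**What the plan says.** SAP section 6.4 builds the clinical benchmark from recurrence by size class: "reoccurrence rates of 14.1%, 24.5%, and 58.1% were reported for the small, medium and large tumor groups". "The benchmark number to be used for the overall group comparison is the weighted average of these proportions with the above recurrence rates", which is given as 24.1%. The lower 95% limit, based on 1817 observations, is q_base = 0.2217.

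Section 6.4.4 starts with a matching kind of quantity: "We wish to average the 2-year survival probability across the study patients". It then offers two ways to handle tumor size. The first is that "we can substitute the mean tumor size for the benchmark population in [4" in place of x_i. The second reads "Alternatively, we may substitute x_i with the corresponding small, medium, and large tumor size subgroup mean", described as closer control. Both are permissive, and no rule selects among the three versions of q_RFA.

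Section 6.4.2 sets the linear predictor to "\log(\lambda_{ik}) = \gamma_k + \beta x_i" and states the assumption that "the effects of all terms other than γ_k does not depend on k". Section 6.2 separately plans to weight the sample to the benchmark's size frequencies.

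**The concern.** In a logistic model, the risk at the average size is generally not the average of the risks. At recurrence rates mostly below one half and rising with size, the curve bends upward, so the risk at the mean lies below the mean risk. The mean-size version of q_RFA would then read low against a benchmark that is itself a mean risk, and the difference would favor the device.

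At stake is the margin that section 6.4 builds in by using the lower confidence limit instead of 24.1%. A difference of definition of the same size would use that margin up without anyone having decided to give it away.

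**Working it through.** **1. Reproduce the benchmark.** Rates are 14.1, 24.5 and 58.1% for small, medium and large (section 6.4). With weights 45.2/41.9/12.9%:

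0.452×0.141 + 0.419×0.245 + 0.129×0.581 = 0.0637 + 0.1027 + 0.0749 = 0.2413.

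Lower limit: 0.2413 − 1.96×√(0.2413×0.7587/1817) = 0.2217. Both printed figures are matched, and the buffer is 1.97 points before rounding.

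This is the reverse of the order printed: "The proportion of cases expected in the small, medium, and large categories are 12.9%, 41.9%, and 45.2% respectively". In printed order the average is 0.0182 + 0.1027 + 0.2626 = 0.3835, with lower limit 0.3611. That discrepancy is a separate matter. The reversed order is used below because it is the one that gives the SAP's figures.

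**2. The printed model.** θ_i4 = exp(γ_4 + βx_i) / Σ_k exp(γ_k + βx_i). The factor exp(βx_i) is common to numerator and denominator and cancels, leaving exp(γ_4)/Σ_k exp(γ_k) at every size. Substituting any size changes q_RFA by exactly 0.

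**3. A model in which size acts.** Take risk(x) = 1/(1 + exp(−(a + bx))), fitted to the three rates by weighted maximum likelihood. The documents give cut-points (3 and 5 cm) but no class means, so class mean sizes are assumed. The plug-in size is taken as the mean of the same mix.

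For 2.5/4/6 cm the fit is a = −3.416, b = 0.602. Mean size = 0.452×2.5 + 0.419×4 + 0.129×6 = 3.58 cm. Risk at 3.58 cm = 22.1%, mean risk = 24.1%, gap = 2.0 points.

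| Assumed class means (cm) | Mean size (cm) | Risk at mean size | Mean risk | Gap (points) |
|---|---|---|---|---|
| 2.5 / 4 / 5.5 | 3.52 | 22.0% | 24.1% | 2.1 |
| 2.5 / 4 / 6 | 3.58 | 22.1% | 24.1% | 2.0 |
| 2.5 / 4 / 7 | 3.71 | 22.3% | 24.1% | 1.8 |
| 2.5 / 4 / 8 | 3.84 | 22.4% | 24.1% | 1.7 |
| 2 / 4 / 6 | 3.35 | 22.0% | 24.1% | 2.1 |
| 2.7 / 3.8 / 6.5 | 3.65 | 22.4% | 24.1% | 1.7 |

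A continuation-ratio model of the kind in section 6.4.5, with a size term added, gives 2.0-2.5 points. With the weights in printed order, the logistic gap over the sizes in the table is 1.9-2.4 points around a mean risk of 38.3%.

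**4. Sensitivity to the plug-in size.** In the 2.5/4/6 cm fit, risk equals 24.1% at (ln(0.2413/0.7587) + 3.416)/0.602 = 3.77 cm. A plug-in mean 0.19 cm above 3.58 cm therefore removes the gap, and a larger one reverses it. Over the six sets the shift needed is 0.17 to 0.25 cm.

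**5. What it could do to a decision.** Section 6.4.6 illustrates power with an exact test. The one-sample exact rule that reproduces its figure is to reject at 8 or fewer recurrences in 62: P(X≤8) = 4.8% at 0.2217 and 80.1% at 0.105. As an approximation, read the risk 1.7-2.1 points low:

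| True average risk | P(X≤8), no shift | P(X≤8), risk read 1.7-2.1 points low |
|---|---|---|
| 24.1% (no effect) | 2.2% | 4.4-5.1% |
| 22.17% | 4.8% | 8.9-10.1% |

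**The case against.** The strongest reply is that nothing goes wrong under the equations as printed. The size term cancels, so the gap exists only after a repair or in the section 6.4.5 fallback, which itself writes out no size term. That stands, and the point is conditional on it. But the SAP plainly means size to act: it calls size a very strong predictor and offers the substitution in order to control for it. Repairing the model while leaving this sentence in place would bring the mismatch in.

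The substitution is also optional. The main definition averages over patients, subgroup means are offered, size may be categorical (section 6.4.1), and section 6.2 promises weighting. This stands too: a reader might infer that the plan mandates a biased estimator, and it does not. The remaining fault is that one of several unranked options does not match the benchmark. Subgroup means close most of the gap only if class risks are then averaged with the benchmark weights, which section 6.4.4 does not state.

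A reader might also infer that a device with no effect would beat the benchmark, with a 9-10% false-positive rate. The figures do not support that. A no-effect device at 24.1% would read 22.0-22.4%, level with 22.17%, and the illustrative rejection rate is 4.4-5.1%, close to the nominal 5%. The 9-10% belongs to a true risk of 22.17%, already about 2 points better than the historical estimate. Nor is either figure the type I error of the planned analysis, which is a posterior probability with no printed decision threshold.

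Finally, only the confidence-interval buffer is touched. Section 6.4 claims further, unquantified conservatism from shorter follow-up in reference [4], and that is unaffected.

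**Conclusion.** The mismatch is real: one permitted version of q_RFA is a risk at a single size, and the benchmark is an average of risks. Its effect is zero under the printed model. With a working size effect it is 1.7-2.1 points in the device's favor, about equal to the 1.97-point confidence-interval buffer.

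That size rests on four assumptions: class means of 2-2.7, 3.8-4 and 5.5-8 cm; the reversed weights; a logistic size effect; and a plug-in mean equal to the mean of the same mix. The mean size in reference [4] is not in the documents, and a value about 0.2 cm larger would remove the gap. So about 2 points is an illustration and not an established bias. The difference in what is being estimated needs no such assumption. The point is worth correcting, most sensibly together with the size term.

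**What to change.** Delete the mean-size substitution from section 6.4.4. Give size a category-specific effect, with one category as reference, or include a size term in the continuation-ratio model. For each posterior draw, compute predicted 2-year recurrence by size or size class, average it over the size distribution used for the benchmark, and compare that average with q_base. Name this as the single primary version of q_RFA.

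State which size distribution is meant: section 6.2 points to the historical data, while section 6.4 takes its proportions from past clinical experience and prints them in an order that does not give 24.1%. The averaging then also delivers the weighting that section 6.2 intends.

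The cost is SAP wording and one averaging line in the posterior code. No further data or patients are needed.

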Although the PGP model prediction is currently equivalent in accuracy to the manufacturer's kill charts, the PGP software provides the immediate advantage of clear visualization of either predicted ablation zone. Even experienced interventional physicians cannot accurately superimpose overlapping volumes when a larger tumor is treated with multiple ablations — and this is an essential function of the software. Participants should benefit from this advantage through better assurance of complete coverage of target tissues and minimization of non-target tissue damage. In turn, this should manifest as a decrease in local recurrence rates, possibly shorter procedure times, and fewer complications.

17 Data Management and Confidentiality

Please reference SF19108 clinical protocol v29July2019, pages 13-18, Section 6.0 Statistical Plan; pages 22-23, Section 8.0 Data Handling and Record Keeping

18 Provisions to Monitor the Data to Ensure the Safety of Subjects

Please reference SF19108 clinical protocol v29July2019, pages 18-22, Section 7.0 Safety and Adverse Events; pages 23-24 Section 9.0 Study Monitoring, Auditing, and Inspecting

19 Provisions to Protect the Privacy Interests of Subjects

All efforts will be made to protect the privacy interests of participants in this study and the personal health information collected as part of this study. Eligible participants will be at DHMC for a scheduled clinical procedure, and all DHMC staff are required to maintain and respect patient privacy in adherence to HIPAA and institutional regulations. Discussions about personal health matters and other personal information will be conducted in private areas, with patient access limited to required clinical staff.

20 Compensation for Research-Related Injury

This research is funded by NE Scientific, LLC through an SBIR Phase II grant (CA189515-03) awarded by the National Cancer Institute and compensation for a research-related injury or illness is not provided by federal law.

If participants are injured or become ill as a result of research procedures, they will be provided with medical treatment but the following organizations do not plan to pay for this treatment:

- Mary Hitchcock Memorial Hospital
- Dartmouth-Hitchcock Clinic

PROTOCOL TITLE: An Intraoperative Guidance Platform for Radio Frequency Ablation

- Dartmouth-Hitchcock Medical Center
- Norris Cotton Cancer Center
- Trustees of Dartmouth College
- NE Scientific, LLC
- National Cancer Institute

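### The size-subgroup recurrence criterion in SAP 6.4.4 holds every tumor size to the one overall benchmark, which is too easy for small tumors and too hard for large ones

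*SAP*

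**What the plan says.** SAP section 6.4 builds the recurrence benchmark from historical rates by tumor size: "reoccurrence rates of 14.1%, 24.5%, and 58.1% were reported for the small, medium and large tumor groups". It combines them with an expected size mix ("The proportion of cases expected in the small, medium, and large categories are 12.9%, 41.9%, and 45.2% respectively") into one overall figure, described as "the weighted average of these proportions with the above recurrence rates, which equals 24.1" percent. It then takes a lower 95% limit, on the ground that "the failure rate data in [4] involve 1817 observations": "we obtain $q_{\text{base}} = 0.2217$ as our ideal or most conservative benchmark". Both values are to be used: the sentence that introduces the hypothesis test begins "For both the conservative and less conservative benchmarks".

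Section 6.4.4 turns to the size subgroups: "we may estimate $\Pr(q_{\text{RFA}} < q_{\text{base}} \mid \text{size} = s, y_1, \dots, y_n, x_1, \dots, x_n)$ separately for each subgroup". The probability is conditioned on size, but the benchmark symbol is the one from section 6.4. The SAP defines no benchmark for a single size stratum and states no posterior probability that would count as success.

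**The concern.** Section 6.4 treats tumor size as a very strong predictor of recurrence, and section 6.2 reweights the sample by size so that it matches the historical data. A size-averaged benchmark suits a size-averaged sample. Within one stratum, the matching comparator is that stratum's own historical rate. An analyst who follows section 6.4.4 literally would apply an overall value three times.

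The null value would then be wrong in opposite directions. A favorable result in small tumors could reflect only that small tumors recur less often. A real benefit in large tumors could go unrecognized. Protocol section 16 makes the second error awkward, because it argues that even experienced physicians "cannot accurately superimpose overlapping volumes when a larger tumor is treated with multiple ablations" and presents this as an essential function of the software.

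**Working it through.** **Inputs, all from SAP section 6.4 unless noted.** Historical recurrence: small 0.141, medium 0.245, large 0.581. Overall benchmark 0.2217 (less conservative 0.241). Historical observations: 1817. Lesions: 62 (section 6.1).

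**1. Reproduce the benchmark.**
- Mix as printed: 0.129×0.141 + 0.419×0.245 + 0.452×0.581 = 0.0182 + 0.1027 + 0.2626 = 0.383. Lower limit: 0.3835 − 1.96×√(0.3835×0.6165/1817) = 0.361. This is not the SAP's figure.
- Mix in reverse order: 0.452×0.141 + 0.419×0.245 + 0.129×0.581 = 0.0637 + 0.1027 + 0.0749 = 0.2413. Lower limit: 0.2413 − 1.96×√(0.2413×0.7587/1817) = 0.2413 − 0.0197 = 0.2217. This matches.

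So 0.2217 belongs to a mix of 45.2% small, 41.9% medium and 12.9% large, which is 28, 26 and 8 of 62 lesions. I use these sizes below.

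**2. Compare each stratum with 0.2217.** This step needs no prior and no cut-off.

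| Stratum | Historical rate | Change that just reaches 0.2217 |
|---|---|---|
| Small | 0.141 | 0.2217/0.141 − 1 = +57% (recurrence may rise) |
| Medium | 0.245 | 1 − 0.2217/0.245 = 9.5% reduction |
| Large | 0.581 | 1 − 0.2217/0.581 = 61.8% reduction |

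Halving the large-tumor rate gives 0.581/2 = 0.2905, still above both 0.2217 and 0.241. Against 0.241 the small rate may rise by 71% (0.241/0.141 − 1), and the large rate must fall by 58.5% (1 − 0.241/0.581).

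**3. Chance of declaring success against 0.2217.** Assumptions: success means a posterior probability above 0.95; lesions are independent; a Beta posterior within the stratum stands in for the SAP's model.
- Small, n = 28, no effect. Two or fewer recurrences are needed under Beta(0.5,0.5) (posterior 0.982 at 2, 0.937 at 3), under Beta(1,1) (0.971 and 0.912), and by an exact one-sided 0.05 test. P(X ≤ 2 | 28, 0.141) = 0.224, against a nominal 0.05.
- Large, recurrence halved, n = 8. With zero recurrences the posterior is 0.958 under Beta(0.5,0.5) and 0.895 under Beta(1,1). Success has probability (1 − 0.2905)^8 = 0.064 under the first, and is impossible under the second or by the exact test.
- Large, recurrence halved, n = 28 (the printed mix, for range): P(X ≤ 2 | 28, 0.2905) = 0.005.

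**4. The same data against each stratum's own rate, Beta(0.5,0.5), n = 28.**
- Small, 4 of 28 (14.3%, about the historical rate): posterior 0.84 against 0.2217, 0.46 against 0.141.
- Large, 8 of 28 (28.6%, about a halving; again the printed mix): posterior 0.20 against 0.2217, 0.999 against 0.581.

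The overall benchmark ranks a null result above a large benefit, and the stratum benchmarks put them in the right order.

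**5. After the fix.** With each stratum tested against its own point rate by an exact one-sided 0.05 test, false success is at most 3.5% in every stratum under either mix. Power for a halving of large-tumor recurrence is 27.5% at n = 8 and 91.6% at n = 28. For a halving in small tumors it is 12.9% at n = 28.

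**The case against.** The strongest reply is that little depends on this analysis. Section 6.4.4 makes it optional, section 6.4.6 says only the primary analysis is powered, and section 6.2 promises subgroup estimates in addition to the overall tests. Section 6.4 also ties the averaged figure to the overall comparison and prints the stratum rates, so a sympathetic analyst might infer a stratum benchmark. This stands as a reason for moderate severity. It does not remove the point: the only benchmark defined is the overall one, the formula uses it, and low power does not excuse a wrong null value. The small-tumor error grows with sample size, to 67% at n = 100 by the exact test.

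Two more replies stand in part.
- In sections 6.4.2 and 6.4.4 the same size term multiplies every outcome category and cancels. Fitted literally, the three subgroup probabilities would be identical. The pattern shown here appears once size has an effect, through a repaired model, separate fits or the alternative in section 6.4.5. Repairing the size term does not repair the benchmark.
- The benchmark and the printed mix disagree. If the printed mix were right and the benchmark became 0.361, a halved large-tumor rate (0.2905) would fall below it. Small and medium tumors (0.141 and 0.245) would then both meet the criterion with no effect. One benchmark still does not serve three strata.

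A reader might also infer that small tumors will be shown to succeed and large tumors cannot succeed, whatever PGP does. The figures do not support that. With no effect, about 78% of trials (1 − 0.224) would not declare success in 28 small tumors, and the 4-of-28 example misses the assumed cut-off. If large-tumor recurrence fell to 10.5%, success at n = 28 would have probability 42%; at 5%, 84%.

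**Conclusion.** The criterion is wrong as written, with moderate severity. For small tumors it is true with no PGP effect. For large tumors a true halving of recurrence leaves it false, and such a halving would be declared a success about 0.5% of the time at n = 28 and between 0% and 6.4% at n = 8.

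The comparison of rates rests only on figures in SAP section 6.4. The 22% false-success figure for small tumors also assumes the 0.95 cut-off, 28 independent lesions and a model in which size has an effect; it is the same under both Beta priors and the exact test. The n = 8 figures depend on the prior and should be read as a range. Neither the overall clinical test nor the sample size is affected, and a reader should not take this as a fault in the primary comparison.

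**What to change.** In SAP section 6.4.4, replace the benchmark in the size-specific probability with a stratum-specific one, q_base,s. Use 0.141, 0.245 and 0.581 from section 6.4 as point benchmarks, or their lower 95% limits if the stratum counts in reference [4] can be obtained. The SAP gives only the total of 1817, so those limits cannot be computed from it. If point benchmarks are used, say that they lack the allowance for uncertainty built into 0.2217.

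Otherwise, report subgroup recurrence with intervals beside the three historical rates, and no test. With about 8 lesions in one stratum, this may be the more useful form.

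In either case, keep 0.2217 and 24.1% for the overall comparison only, and note that the stratum rates come from variable follow-up, not a fixed 2 years. The cost is a line or two of SAP wording and three constants in the code, with no extra data or patients. The change should be made before outcomes are seen. The cancelled size term and the order of the size mix need their own corrections.
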